1.0 Background

Patients that undergo inner ear surgery often complain of postoperative nausea and vomiting (PONV) despite prophylactic antiemetic regimens with 5HT3 antagonists, steroids and vigorous hydration. Patients still experience this unpleasant feeling that may prolong hospital stay and can lead to nutritional issues such as dehydration and huge patient and family dissatisfaction. We would like to explore the use of regional anesthesia and potential antiemetic properties and compare its efficacy to the existing therapy.

PONV is an unpleasant complication following anesthesia, it is well known that patients undergoing certain surgical procedures such as those involving the inner ear, the tympanomastoid cells, and the cochlear organ may be more prone to PONV. This complication can be anticipated in those instances and prophylactically treated with antiemetics, Vigorous hydration and cautious selection of anesthetic technique and avoidance of drugs known to promote nausea^{1,2,3}. Despite all the measures described above, vomiting still occurs often, leaving patients and their families wondering if more can be done^{4,5}.

Regional anesthesia has a therapeutic and preventive role in the incidence of PONV by reducing post-operative pain and opioids consumption.

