Group C: Will receive both a homolateral or bilateral if surgery involves both ears, a regional block at Erb's point (superficial cervical plexus block) and will receive an anti-emetic drug regiment comprising of dexamethasone 150mcg/kg IV (max dose of 10 mg) and ondansetron 150mc/kg IV (max single dose of 4 mg) at any time after induction of anesthesia and as soon as an intravenous line is available. If, at the anesthesiologist's discretion, ondansetron is re-dose at the end of procedure, a max total dose of 8 mg may be given.

All three groups will receive a standardized general anesthetic regiment, prior to induction the patient *might* require an oral dose of versed 0.5mg/kg as premedication for separation anxiety. Patients will also receive induction of anesthesia either inhalational oxygen in sevoflurane or intravenous induction if subject patient has an IV access, muscle relaxants will be avoided to preserve facial nerve monitoring as required by the surgical approach. Anesthesia will be maintained with oxygen in sevoflurane or desflurane. Prior to emergence of anesthesia and at any point during the procedure, patients may receive IV analgesics (acetaminophen, morphine, fentanyl, ketamine) for postoperative analgesia according to the standard recommended pediatric dosing regiments commonly used at Riley Hospital.

All three groups will receive the standard PACU protocol for pain management and anti-nausea and vomiting intervention. Following patient's recovery starting upon emergence (t_0), all symptoms indicating nausea and/or vomiting and pain will be recorded and every 15min (t_{15}) thereafter in PACU than every 4-6 hrs. while on the inpatient unit for 24 hrs and will be treated as deemed necessary. For pain assessment a FLACC scale and Visual Analogue Scale (VAS) will be used. Complaints of, or signs or symptoms of, nausea, retching and/or vomiting will be documented in the PACU or floor for 24 hours post-operatively. For patients discharged to home prior to the 24 hours, follow up will be done by phone call using the Rhodes INRV to report post-operative nausea and vomiting.

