We will also review patients chart for requests or demands for any pain medications and anti-emetics, documentation of their usage as well as times of discharge from the recovery room to the floor and their discharge from the hospital. For cost comparison and analysis we will look at itemized billing for medical services related to anesthesia, pharmacy use and IV fluid use, antiemetic interventions, medication for pain throughout hospital stay from recovery room to time of discharge from the hospital. For patients that are discharged the same day of their surgery they will be given The Rhodes INRV survey to fill out at home and will be called by phone the following day to collect that information.

A cost analysis between the three study groups taking into account all the items above will be done to compare overall cost of care between the three study groups.

6.0 Reporting of Adverse Events or Unanticipated Problems Involving Risk to Participants or Others

Risk related to the Blocks

Bleeding

Infection at the site

Intravascular local anesthetic injection

Anaphylactic/allergic reaction

Rare spread of local to deeper structures, inadvertent Phrenic nerve blockade (the injection are superficial, subcutaneous with specific landmarks)

Failure of the block to produce pain relief or to prevent nausea and vomiting

Complications related to the surgical procedure including but not limited to:

Facial nerve blockade

Risk of General Anesthesia

All precautions will be taken care of to avoid the above complications by adhering to standard of practice with strict adherence to standard ASA monitoring will be used at all time, observance of the time out procedure and surgical site marking, using universal precautions for sterility and observance of safe injection technique for the regional blocks with intermittent aspiration and injection to avoid intravascular injection and use of live imaging with ultrasound guidance if necessary.

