1. Great auricular nerve
 2. Lesser occipital nerve
 3. Auricular branch of vagus nerve
 4. Auriculotemporal nerve

[figure not shown]
Ear Innervation

Superficial Cervical Plexus Anatomical Relations and Injection Site

Vagus Nerve (X)

RHODES INDEX OF NAUSEA, VOMITING AND RETCHING

Patient initials _____

Date _____

[figure not shown]
Day of week _____

Time of day _____

[figure not shown]
Directions: Please mark the box in each row that most clearly corresponds to your experience. Please make **one** mark on **each line**.

1. In the last 12 hours, I threw up ____ times.	7 or more	5-6	3-4	1-2	I did not throw up
2. In the last 12 hours, from retching and dry heaves, I have felt ____ distress.	no	mild	moderate	great	severe
3. In the last 12 hours, from vomiting or throwing up, I have felt ____ distress.	severe	great	moderate	mild	no
4. In the last 12 hours, I have felt nauseated or sick to my stomach.	not at all	1 hour or less	2-3 hours	4-6 hours	more than 6 hours
5. In the last 12 hours, from nausea/sickness to my stomach, I have felt ____ distress.	no	mild	moderate	great	severe
6. In the last 12 hours, each time I threw up, I produced a ____ amount.	very large (3 cups or more)	large (2-3 cups)	moderate (1/2-2 cups)	small (up to 1/2 cup)	I did not throw up
7. In the last 12 hours, I have felt nauseated or sick to my stomach ____ times.	7 or more	5-6	3-4	1-2	no
8. In the last 12 hours, I have had periods of retching or dry heaves without bringing anything up ____ times.	no	1-2	3-4	5-6	7 or more

Copyright 1996. Curators of Missouri. [name], EdS, FAAN

Superficial cervical Plexus infiltration

Nerve of Arnold Injection

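### Analgesic and antiemetic use is recorded only up to hospital discharge, so the observation window varies by child and can differ between arms if discharge timing does

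*Combined protocol and SAP*

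**What the plan says.** Three parts of Section 5.0 (Study Procedures) bear on this.

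- **Drug use.** The source is the chart: "We will also review patients chart for requests or demands for any pain medications and anti-emetics, documentation of their usage". The billing items for the cost comparison cover antiemetic interventions and "medication for pain throughout hospital stay from recovery room to time of discharge from the hospital". No source of drug data after discharge is named.
- **Symptoms.** Nausea, retching and vomiting "will be documented in the PACU or floor for 24 hours post-operatively". This continues after discharge: "For patients discharged to home prior to the 24 hours, follow up will be done by phone call using the Rhodes INRV".
- **The call.** Section 5.0 expects some children to leave on the day of surgery ("For patients that are discharged the same day of their surgery"). They take the Rhodes form home and "will be called by phone the following day to collect that information", that information being the Rhodes answers.

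The Rhodes form at the end of the document has eight items on vomiting, retching and nausea, of the type "In the last 12 hours, I have felt nauseated or sick to my stomach". None asks about a drug taken.

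Section 1.0 (Background) says that persisting nausea and vomiting may lengthen the hospital stay. It also says: "Regional anesthesia has a therapeutic and preventive role in the incidence of PONV by reducing post-operative pain and opioids consumption".

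**The concern.** Symptoms have a fixed 24-hour window and drug use does not. Each child's drug record is as long as that child's stay, and by the plan's own account the stay can depend on nausea and vomiting, which the trial compares. If one arm tends to go home sooner, its charted analgesic and antiemetic use can be lower even when 24-hour need is the same. A reader could take that for a sparing effect of the block, particularly as Section 1.0 links regional anesthesia to lower opioid consumption. The charted totals alone could not separate the two explanations.

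There is also a smaller problem of interpretation. An antiemetic taken at home leaves no trace, so the Rhodes answers of a child sent home cannot be read alongside treatment, as an inpatient's symptoms can.

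**Working it through.** **The plan's own figure.** Section 8.0 gives 20 per group for nausea/vomiting of 90% vs 50%, two-sided 5%, 80% power. With pooled variance, no continuity correction and one pairwise comparison:

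n = [1.96·√(2·0.7·0.3) + 0.8416·√(0.9·0.1 + 0.5·0.5)]² / 0.4² = (1.270 + 0.491)² / 0.16 = 19.4, so 20 per group (power at 20: 81.3%).

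The figure reproduces. It concerns nausea/vomiting only, and nothing below changes it.

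**Inputs for the drug-use window.** The documents give no length of stay, share discharged on the day, or amount of drug use. The following are assumptions:

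- true 24-hour use is the same in both arms and falls at a constant rate;
- a share f of an arm goes home on the day, at hour h, with h from 4 to 8;
- all other children are observed for the full 24 hours.

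**Mean charted window.** W = f·h + 24·(1 − f). With constant, equal use, the ratio of charted use is W₂/W₁.

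| Same-day share, arm 1 vs arm 2 | h = 4 | h = 6 | h = 8 | Apparent reduction |
|---|---|---|---|---|
| 25% vs 75% | 9.0/19.0 = 0.474 | 10.5/19.5 = 0.538 | 12.0/20.0 = 0.600 | 40-53% |
| 25% vs 50% | 14.0/19.0 = 0.737 | 15.0/19.5 = 0.769 | 16.0/20.0 = 0.800 | 20-26% |
| 50% vs 50% | 14.0/14.0 = 1.00 | 15.0/15.0 = 1.00 | 16.0/16.0 = 1.00 | none |

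In the last row the arms are comparable, but both are under-counted: 14/24 to 16/24, or 58-67% of true use, is seen.

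**Any use (yes/no).** Assume a true 24-hour rate of 60% in both arms and exponential time to first use. The probability of use by hour h is 1 − 0.4^(h/24): 0.142 at h = 4 and 0.263 at h = 8. The charted rate is f·(that value) + (1 − f)·0.60.

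- 25% same-day: 0.25·0.142 + 0.75·0.60 = 0.485, up to 0.25·0.263 + 0.75·0.60 = 0.516.
- 75% same-day: 0.75·0.142 + 0.25·0.60 = 0.256, up to 0.75·0.263 + 0.25·0.60 = 0.347.

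The same true 60% would be charted as about 49-52% in one arm and 26-35% in the other.

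**Dependence on timing.** Let e be the share of 24-hour use that falls before same-day discharge. The ratio is then [1 − f₂(1 − e)] / [1 − f₁(1 − e)]. Constant use sets e = h/24, which gives the table. As use concentrates soon after emergence, e approaches 1 and so does the ratio.

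**The case against.** The strongest reply is that the plan never sets up the comparison that would be biased. Drug use is not a named endpoint and has no stated test, and Section 8.0 powers nausea/vomiting only. The one stated between-arm use of these data is the cost analysis, where a window from recovery room to discharge is explicit and suits itemized hospital billing. This stands. It limits the concern to drug use read as a sign of efficacy, and to home drugs being left out of the costs.

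Section 5.0 also records times of discharge from the recovery room and from the hospital. Each child's window is therefore known, and use could be compared in the recovery room, over a shared early period, or per hour. This also stands in part: it eases the unequal-window problem but cannot recover home doses, and the plan does not say that any such comparison will be made.

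Three stronger readings are tempting, and the documents do not support them.

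- *Opioid sparing is the hypothesis under test.* The sentence in Section 1.0 is background. The mechanism hypothesised in Section 2.0 is blockade of the auricular branch of the vagus, and the outcome that bears on it is nausea and vomiting.
- *A child discharged at hour 6 loses 75% of drug use.* 18/24 = 75% is a share of time. It is a share of use only if use is evenly spread.
- *Unrecorded home antiemetics invalidate the Rhodes result.* The items ask whether and how often symptoms occurred in the last 12 hours, so a child who was sick in that period and then treated still reports it. Only a dose that prevented symptoms would be hidden.

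**Conclusion.** The gap in data capture is certain on the text. Drug use ends at discharge, symptoms do not, and neither the Rhodes form nor the described call closes the difference. Windows therefore differ between children.

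A reader might infer that the arms will be compared over unequal windows and that their drug-use results will be biased. The documents do not go that far. Arms differ only if discharge timing differs by arm, which Section 1.0 makes plausible but nothing quantifies. The false reductions of 40-53% and 20-26% show what is possible under assumed same-day shares, same-day discharge at 4-8 hours and constant use. They are not estimates for this trial; equal shares give no between-arm bias, and early use makes it smaller.

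The sample size and the powered outcome are unaffected. The point is worth acting on because the correction is cheap and home doses cannot be reliably recovered later.

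**What to change.** In Section 5.0:

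1. Add two questions to the next-day call: any antiemetic taken since discharge, and any pain medicine taken since discharge. For each, record the drug, the number of doses and whether it was given for symptoms.
2. State a common window for drug use of 0-24 hours after emergence, matching the symptom window, and report use over it by arm.
3. Keep the recovery-room-to-discharge totals as well. The cost analysis needs them, and a 24-hour window would drop later inpatient use.
4. Report home antiemetic use beside the Rhodes result. Do not redefine the nausea/vomiting outcome by home doses alone: that could count a precautionary dose as an event and would treat children at home differently from inpatients.

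The cost is two questions on a call already planned and the matching fields on the data sheet, with no extra staff. The downside is that home doses rest on parental recall, over less than about a day.

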2.0 Rationale and Specific Aim

We would like to compare the therapeutic and cost effectiveness of established therapies for postoperative nausea and vomiting to regional nerve blocks of the head and neck area an intervention known for analgesia but for which the antiemetic effects hasn't been entirely explored.

Our rationale is based on the knowledge of the anatomical innervation of the inner ear and the role of the parasympathetic nervous system in the emetic act. A lot of focus has been given on its counterpart the sympathetic nervous system and its role in painful conditions. We believe that the nerve blockade of the parasympathetic innervation can have some beneficial effect in the post-surgical patient.

The role of the vagal nerve response in the act of vomiting has been extensively studied. Observation that the Vagus nerves are predominantly sensory nerves has been shown through direct electrophysiological recordings of this afferent traffic from the vagal distribution in the GI tract to the brain stem. Vagal afferent terminals stained with horseradish peroxidase (HRP) appear to project to the dorsal motor vagal nucleus (DMVN) and to the area postrema. This latter projection may provide a visceral input for vomiting^{1,2,3}. In fact electrical stimulation of vagal afferent fibers readily evokes vomiting in experimental animals. Furthermore, stimulation of the concha of the ear which is innervated by the (sensory) auricular branch of the Vagus nerve produced activation of the solitary nucleus and its following projections: parabrachial nucleus, thalamus, amygdala, paracentral lobule, and insula shown during fMRI^{1,2,3}

This latter distribution is of interest to our study since it involves the area of surgery where the auricular branch of the vagus nerve should easily accessible for anesthetic blockade.

There shouldn't be a surprise that most of the anti-emetics in use today have a mechanism of action that involves the modulation of the vagal effect during the emetic act^{1,2,3}.

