4.0 Enrollment/Randomization

Subject will be approached by [name], the surgeon at his office the day of the preoperative office visit appointment or by any member of the study team the day of the surgery in the preoperative area.

After appropriate assent and consent is obtained subject will be given an identifier and will undergo randomization using a computer program.

Subject will be assigned to either one of the three groups.

Study will involve pediatric patients Age 1-18 years old who are scheduled to undergo inner ear surgery. Subjects will be randomization into three different groups. Each group will consist of 20 patients; we intend to enroll 60 participants total.

Group A Nerve of Arnold block with superficial cervical plexus block (SCPB)

Group B IV dexamethasone (Decadron) + ondansetron (Zofran)

Group C Block + IV dexamethasone (Decadron + ondansetron (Zofran)

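### The cost comparison rests on itemized billing with no step from billed amounts to costs, so unequal departmental mark-ups could distort, and possibly reverse, the Group A versus Group B result.

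*Combined protocol and SAP*

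**What the plan says.** Section 2.0 makes cost part of the aim: "We would like to compare the therapeutic and cost effectiveness of established therapies", set against regional nerve blocks. Its last paragraph repeats the intention.

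Section 5.0 names the data source: "For cost comparison and analysis we will look at itemized billing for medical services related to anesthesia". The list continues with "pharmacy use and IV fluid use, antiemetic interventions, medication for pain throughout hospital stay from recovery room to time of discharge from the hospital". The stated use is: "A cost analysis between the three study groups taking into account all the items above will be done to compare overall cost of care". Just before this, section 5.0 plans a chart review of requests for and use of pain medication and antiemetics, and of discharge times from the recovery room and the hospital.

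Section 4.0 defines the arms. Group A has nerve blocks, Group B has intravenous dexamethasone and ondansetron, and Group C has both.

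No section gives unit costs, a cost-to-charge ratio, a costing perspective or a price year, or says that the result will be labelled as charges. Section 8.0 covers only the sample size for nausea and vomiting. Beyond that, sections 8.0 and 11.0 say only that the data will go for statistical analysis.

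**The concern.** A billed amount is a cost multiplied by a mark-up, and the mark-up may differ from one department to another. Items common to all arms, such as the general anesthetic, fall out of the between-arm difference on average. What remains is what the arms do differently. Here that is a procedure in Group A against pharmacy items in Group B. If the two departments mark up differently, the billed difference between A and B mixes a cost difference with a pricing difference. Randomisation does not balance this out, and more patients would not help, because the pricing goes with the assigned treatment.

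At stake is the cost half of the stated aim: the trial could name as cheaper an arm that is not.

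A second ambiguity sits in the same sentence. Its closing clause limits something to the period from the recovery room to hospital discharge, but the sentence does not show whether that limit covers the whole list or only the pain medication. The initial block, any repeat block and the study antiemetics are all given in the operating room.

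**Working it through.** **Figures in the plan.** The plan states no cost figure, so there is none to reproduce. Its one design figure, 20 per group for 90% versus 50% at two-sided 5% and 80% power (section 8.0), does reproduce: the usual two-proportion formula without continuity correction gives 20, with 81.3% power. It has no bearing on cost.

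**Inputs.** From the documents: the resource type in each arm (section 4.0) and the source of the money data (section 5.0). Assumed, because the documents give no prices: block cost *K* = 60, drug cost *D* = 40, and mark-ups *m*K (procedure) and *m*D (pharmacy).

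**Group A minus Group B, intervention items only.**

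- Cost difference = *K* − *D* = 60 − 40 = +20 (block dearer).
- Billed difference = *m*K × *K* − *m*D × *D*.
- With equal mark-ups *m*, this is *m* × (*K* − *D*), so the sign never changes.
- When *K* > *D*, the sign flips if *m*D / *m*K > *K* / *D* = 60 / 40 = 1.5.

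| *m*K | *m*D | ratio *m*D/*m*K | billed A − B | direction |
|---|---|---|---|---|
| 2 | 2 | 1.0 | 120 − 80 = +40 | kept |
| 3 | 2 | 0.67 | 180 − 80 = +100 | kept, inflated |
| 2 | 3 | 1.5 | 120 − 120 = 0 | threshold |
| 2 | 4 | 2.0 | 120 − 160 = −40 | reversed |
| 1.5 | 6 | 4.0 | 90 − 240 = −150 | reversed |

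**The other direction.** Suppose instead that the block arm costs 100 in services plus 20 in drugs = 120, and the drug arm costs 140 in drugs and rescue. The block arm is then cheaper by 20. The extra service is 100 and the extra drug cost is 140 − 20 = 120, so reversal needs a service-to-drug mark-up ratio above 120 / 100 = 1.2.

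- Mark-ups 3 and 3: 300 + 60 = 360 against 420, ranking kept.
- Service 4, drug 3: 400 + 60 = 460 against 420, ranking reversed.
- Service 2, drug 4: 200 + 80 = 280 against 560, ranking kept, although the same pair reversed the first example.

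**How far the assumptions matter.** With procedure mark-ups of 1.5 to 3 and pharmacy mark-ups of 2 to 6, *m*D/*m*K runs from 2 / 3 = 0.67 to 6 / 1.5 = 4. Within those ranges no reversal is possible if the block costs more than 4 times the drugs, or less than two-thirds of them. The documents do not show where the true ratio lies.

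**Comparisons with Group C.** Take Group C as Group A's block plus Group B's drugs, as section 4.0 lists it. On intervention items, C − A = *m*D × *D* and C − B = *m*K × *K*. Both are positive for any positive mark-ups, as they are by cost. Reversal therefore needs downstream savings in C that offset the added item. (The Group C paragraph in section 5.0 names only the plexus block; this should be reconciled with section 4.0 before costing.)

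**The counting window.** If the recovery-room-to-discharge limit governs the whole list, neither *K* nor *D* is counted. On the assumed figures the comparison would leave out 60 − 40 = 20 for A versus B, 40 for C versus A and 60 for C versus B. Mark-ups would then act only on downstream items such as rescue drugs, analgesics, fluids and recovery services. If the limit governs only pain medication, the block and study drugs may be counted under anesthesia services and pharmacy, and the algebra above applies directly.

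**The case against.** The best reply is that the plan never says billed amounts will be the cost measure. Itemized bills can serve as a list of what was used, and the chart review already collects use of pain medication and antiemetics and discharge times. On that reading the quantities are partly planned and only the valuation is unstated. This is fair as far as it goes. But billing is the only monetary source named, it is introduced for the cost comparison, and no other way of valuing resources appears. Nor does the plan say whether charged, allowed or paid amounts are meant.

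The reply is also right on several limits, and a reader might infer more than the documents support:

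- *That the trial will report a pricing artefact.* Every price and mark-up above is assumed. The documents support only that it could.
- *That mark-ups cancel only when the arms use the same mix of resources.* Equal mark-ups across departments also preserve the ranking, whatever the mix.
- *That any pair of arms could reverse in the same way.* On intervention items alone, only A versus B can.
- *That the arms split cleanly into procedure and pharmacy.* The block itself uses bupivacaine, in part with epinephrine, so some pharmacy content sits on both sides.

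Finally, the trial is sized for nausea and vomiting, and that result is untouched. This limits the weight of the point but does not remove it, because cost effectiveness is a stated aim.

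**Conclusion.** The concern holds in conditional form. Section 5.0 would support a conclusion on overall cost of care from billing data without any conversion to cost. Distortion of A versus B requires two things: that billed amounts are used as the measure, and that mark-ups differ between departments. A change of direction further requires that the mark-up ratio crosses the ratio of true costs, which is 1.5 in the first assumed example and 1.2 in the second. The two examples reverse in opposite directions, so a reader of the results could not guess the bias and correct for it. The real size and direction cannot be given from these documents.

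The counting window is a separate gap in the same sentence. On the narrow reading the mark-up problem shrinks to downstream items, but the comparison then omits the cost of the interventions being compared.

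The efficacy comparison is unaffected. The change is worth making because the remedy is cheap and better than the stated method, not because a wrong answer has been shown.

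**What to change.** Amend section 5.0 to say that:

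- itemized bills and chart review will be used to count resources (block procedures, study drug doses, rescue drugs, analgesics, fluid units), explicitly including the randomised block and study antiemetics given in the operating room;
- each resource will be valued with one fixed unit-cost list applied to every child, or each charge will be multiplied by its department's cost-to-charge ratio;
- the costing perspective and the start and end of the counting period are fixed before the data are analysed.

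If neither unit costs nor ratios can be obtained, report the result as a comparison of billed charges and draw no conclusion on cost.

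This takes a short list or set of ratios from the finance office and a sentence or two of protocol text. Treatment, enrolment and what is asked of the children and families do not change. The downside is a little extra costing work, and the unit costs are local, so the result may not carry over to other hospitals.

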We hypothesize another potential antiemetic mechanism by the blockade of the auricular branch of the Vagus nerve at the ear canal (commonly described as nerve of Arnold) in conjunction with a block of the greater auricular nerve and lesser occipital nerve at the superficial cervical plexus level^{8,9,10}. The block would cover both the sensory innervation and of the ear canal and the inner ear. A regional anesthetic block prior to the surgical intervention on the inner ear at the superficial cervical plexus block is performed. This latter is a branch of the vagus nerve at the superficial cervical plexus (erb's point). The block would inhibit the vagal afferent to area postrema through inhibition of afferent vagal input to the medullary center.

The emetic act (vomiting) is a highly integrated physiologic reflex involving both the somatic and autonomic nervous system. We do not know how much of a relation there is between the vagal nerve branches involvement and incidence of nausea and vomiting effects are from the inner ear injury and or the inflammatory response type of response triggering the area postrema. The usual prophylactic treatment of PONV has been limited to anti-emetics such 5-HT3 and dexamethasone^{6,7}, along with aggressive fluid therapy and adequate analgesia.

We are proposing to conduct a comparative study of the therapeutic and cost effectiveness of regional anesthesia and antiemetic therapy in the prevention and treatment of PONV in children undergoing inner ear surgical procedures.

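### Costs are counted only to hospital discharge but PONV is followed to 24 h, so care after an early discharge goes uncosted and can bias the cost comparison, in an unknown direction

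*Combined protocol and SAP*

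**What the plan says.** All of this is in the combined protocol and SAP.

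- **Aim.** Section 2.0 proposes a "comparative study of the therapeutic and cost effectiveness of regional anesthesia and antiemetic therapy". Section 5.0 undertakes to "compare overall cost of care between the three study groups".
- **Cost source and period.** Section 5.0: "For cost comparison and analysis we will look at itemized billing for medical services related to anesthesia, pharmacy use and IV fluid use". The list of items goes on to antiemetic interventions and ends with "medication for pain throughout hospital stay from recovery room to time of discharge from the hospital". No other cost period is stated.
- **PONV period.** Section 5.0 records symptoms for 24 h after surgery, starting at emergence. "For patients discharged to home prior to the 24 hours, follow up will be done by phone call using the Rhodes INRV". Of children who go home on the day of surgery it says that "they will be given The Rhodes INRV survey to fill out at home and will be called by phone the following day". The stated purpose of that call is to collect the survey answers.
- **Home instrument.** The Rhodes form at the end of the document has eight items. They ask how often, how long, how much and with what distress the child had nausea, retching or vomiting.
- **PONV and stay.** Section 1.0 says that PONV "may prolong hospital stay and can lead to nutritional issues such as dehydration".

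**The concern.** A comparison of cost and effect should count both over the same period. Here the two periods end at different times for any child who goes home before 24 h. If a child on the ward vomits at 18 h and receives fluid and an antiemetic, the treatment is billed and counted. If a child already at home vomits at 18 h and is brought back or treated, the symptoms reach the Rhodes form but the care adds nothing to the cost.

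Discharge time is decided after randomisation, and section 1.0 itself links it to PONV. Treatment can therefore change how long a child's costs are counted. What is at stake is the cost half of the stated aim, not the PONV comparison.

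**Working it through.** **1. The plan's own figure.** Section 8.0 gives 20 per group for 80% power, 90% against 50%, two-sided 5% chi-square. With pooled variance and no continuity correction:

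n = [1.96 × √(2 × 0.7 × 0.3) + 0.842 × √(0.9 × 0.1 + 0.5 × 0.5)]² / 0.40² = (1.270 + 0.491)² / 0.16 = 19.4, so 20 per group. Power at 20 is 81.3%.

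The figure reproduces for one pairwise comparison. It concerns PONV only and gives no sample-size basis for cost. It is used below only for the arm size of 20, which section 4.0 also states.

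**2. The two periods side by side.**

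- Child in hospital at 24 h: PONV recorded to 24 h; cost counted to discharge. All care up to 24 h is costed.
- Child discharged before 24 h: PONV recorded to 24 h; cost counted to discharge. Care between discharge and 24 h is not costed.
- Child kept beyond 24 h: cost goes on accruing after PONV recording ends, so the mismatch also runs the other way.

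**3. Whether anything else closes the gap.** None of the eight Rhodes items asks about medication, visits or readmission. The chart review in section 5.0 covers requests for and use of pain medication and antiemetics, and discharge times. No section names a source for care after discharge.

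**4. Effect of one missed episode.** If an arm of 20 has m uncounted episodes, each costing X, its mean is too low by m × X/20. One episode gives 0.05X and two give 0.10X. The difference between two arms shifts by (m₁ − m₂) × X/20, which is zero when both arms miss the same number.

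**5. Illustrative range.** The documents give no early-discharge share, rate of later care or price, so the following are assumptions. Let q be the share leaving before 24 h, p the PONV rate after discharge, k the chance that a case needs care, and X its cost. The omitted mean cost per child is q × p × k × X. Using the planning rates of 90% and 50% for p is generous, because some PONV occurs before discharge. With the same q and k in both arms, the omitted costs differ by (0.90 − 0.50) × q × k × X = 0.40 × q × k × X:

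- q = 0: 0
- q = 0.25, k = 0.05: 0.005X
- q = 0.5, k = 0.10: 0.02X
- q = 1, k = 0.25: 0.10X

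In this case the arm with more PONV has more cost left out, so its extra cost is understated.

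**6. Direction.** That sign depends on q being equal. Keep k = 0.10, but let q be 0.25 in the 90% arm and 1 in the 50% arm, as might happen if less PONV means earlier discharge. The omitted means are 0.25 × 0.90 × 0.10 = 0.0225X and 1 × 0.50 × 0.10 = 0.050X. The larger omission is now in the arm with less PONV, by 0.050X − 0.0225X = 0.0275X. With equal k the sign turns when the ratio of the two q values passes 0.90/0.50 = 1.8. Section 8.0 does not say which group has which rate, so the illustration cannot be tied to a named arm.

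**The case against.** The strongest reply is that this is a choice of perspective. An in-hospital cost analysis is legitimate, section 5.0 lists its items, and going home sooner is a real saving as well as a shorter counting period. That stands, but the plan does not say that it takes an in-hospital perspective, and its description of the comparison is wider than what it counts.

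Two readings of the text might rescue it. The words on discharge may attach only to pain medication; even so, no other period and no source after discharge is given. The cost analysis is to draw on everything listed before it, which could include the Rhodes survey; but that survey holds nothing that can be priced.

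A third reply is that bias between arms needs three things: early discharges, care after discharge, and a difference between arms in that care. The documents give a rate for none of them. This stands, and it limits the point to a possible bias.

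A reader might go further and infer that the block arms will look falsely cheap, because the block is given before incision and wears off after the child is home. The documents do not support this. The repeat injection for operations over 4 h suggests that the block is time-limited, but no duration of antiemetic effect is given for the block or for either drug. Group C receives the drugs as well as the block. Nothing shows that block arms fail later than Group B.

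**Conclusion.** The mismatch is in the current text and no section closes it. Care for PONV after an early discharge is left out of the cost comparison, and this can bias the difference between arms.

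The documents fix neither direction nor size. The effect is zero if no child leaves before 24 h, if none needs later care, or if the arms miss equal amounts. Otherwise each uncounted episode lowers its arm's mean by X/20. Under the assumptions shown, with equal early discharge and equal need for care, the arms' omitted costs differ by 0 to 0.10X; unequal early discharge can reverse the sign.

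A reader might want to express the shift as a percentage of the average bill. That needs a ratio of X to the bill, and the documents contain no prices, so any such percentage would rest on the multiplier chosen. Nor do they define how a Rhodes form becomes a PONV case, so the point rests on the two periods and not on case counts.

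This is a cheap improvement to a secondary part of the plan. It does not affect the sample size or the PONV comparison.

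**What to change.** In section 5.0, under the cost comparison:

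1. Count costs for every child to the later of hospital discharge and 24 h after emergence. In the same sentence, say whether the block and the drugs given in theatre are included, since a start at the recovery room could be read as leaving them out.
2. Add to the planned next-day call: since discharge, has the child had any unplanned clinic or emergency visit, any readmission, or any antiemetic?
3. Add the billing for any such care to that child's cost, with a standard price, fixed in advance, for care given elsewhere.

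If this is not done, restate the objective and the comparison as in-hospital cost only.

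The cost is one or two questions on a call already planned and a longer billing query for a few children. Treatment, visits and sample size do not change. There are limits. Care elsewhere may be known only from the family, and a single next-day call will miss later readmissions. A child kept beyond 24 h will still accrue cost after PONV recording ends, so the periods are brought closer but are not identical.
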